## 2.0 ABBREVIATIONS AND TERMS

- AE – Adverse Event
- CRO – Contract Research Organization
- CTF – Cut-to-fit; a barrier hole opening that is cut to size.
- DET score; Validated Ostomy Skin Tool [1]. The DET score assesses Discoloration, Erosion, and Tissue Overgrowth of the peristomal skin.
- eCRF – Electronic Case Report Form
- EDC – Electronic Data Capture; a method used for electronic documentation of study procedures and data.
- EC – Ethics Committee
- HIPAA – Health Insurance Portability and Accountability Act; a US law designed to provide privacy standards to protect patients' medical records and other health information provided to health plans, doctors, hospitals and other health care providers.
- IRB – Institutional Review Board
- MEDDEV – Medical Device Directives (guidance documents) provided by the European Commission
- Peristomal Skin; the skin covered by the adhesive portion of the pouching system (barrier and tape).
- PSC – Peristomal Skin Complication; For the purposes of this study, a peristomal skin complication, is defined as a DET score of greater than 0 due to anything other than normal post-operative healing and/or scar tissue, or an increase in the subject's DET score as compared to the DET score at the prior visit as determined by a study investigator.
- PHI – Protected Health Information; any information about health status, provision of health care, or payment for health care that can be linked to a specific individual.

- **Stoma-related cost;** costs assigned to utilization data accrued through the duration of the study period (including both [REDACTED] and [REDACTED]). This includes treatments related to stoma and/or PSCs (topical medications, clinic visits, accessory use, etc.), social impact of stoma and/or PSCs (e.g. missed work/appointments), hospitalizations, ER visits, physician/clinic visits, ostomy-related medication use and therapies, and barrier utilization.

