### 5.2 SECONDARY OBJECTIVE

The secondary objective of the study is to compare incidence of PSCs in subjects using [REDACTED] to subjects using the control barriers [REDACTED].

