## 7.0 STUDY DESIGN

The study is multi-center, randomized, controlled, double-blinded, and utilizes an adaptive design.

Subjects who meet the Eligibility Criteria (listed in Sections 8.1 and 8.2) are enrolled and randomized to Arm 1 or Arm 2 during the Initial [REDACTED] Visit. The assigned Arm and the study barrier are double blinded. All subjects receive standard clinical management of stoma needs as per the Investigator's usual practices. Subjects are initially enrolled into the [REDACTED] which consists of two study visits after enrollment [REDACTED]. If the subject develops a PSC, as defined as a DET score greater than 0 due to anything other than normal post-operative healing and/or scar tissue, or an increase in the subject's DET score as compared to the DET score at the previous visit, prior to the end of the [REDACTED], the subject will be immediately moved to the four (4) week [REDACTED].

which consists of two study visits [REDACTED]. Thus, the total possible time of participation in the study is up to 12 weeks and up to 5 scheduled study visits.

Subjects in Arm 1 are assigned to the [REDACTED] barrier (Test) and subjects in Arm 2 are assigned to either the [REDACTED] barrier (Control).

Study visits consist of a physical evaluation and photography of the stoma area with the pouching system removed [REDACTED], a structured interview by the investigator or designee [REDACTED], and subject completion of a paper or online Quality of Life questionnaire [REDACTED] provided in the subject's local language. The duration of each study visit is approximately 30 minutes.

In support of the primary objective, the following utilization information is collected to support cost of care calculations: utilization of treatments related to stoma and/or PSCs (topical medications, clinic visits and accessory use), social impact of stoma and/or PSCs (missed work/appointments), stoma and/or PSC related hospitalizations, ER visits, physician/clinic visits, medication use and therapies, and barrier utilization (not including pouch utilization). This data is collected at each study visit through the use of [REDACTED] and may include documentation on [REDACTED].

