In support of the secondary objective, the following clinical information is collected: the Investigators evaluation of the subject's peristomal skin at all in-person visits, including the [REDACTED] Visits, [REDACTED] Visits and any extra visits, if necessary. Each clinical evaluation consists of a visual assessment of the stoma and peristomal skin, rating on the DET scale [1], and photographs. This data is collected using [REDACTED].

[REDACTED]

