## 8.0 STUDY SUBJECTS

### 8.1 INCLUSION CRITERIA

1. At least 18 years of age
2. Have a colostomy, ileostomy, or urostomy
3. Less than or equal to 12 weeks post-op from stoma creation or stoma relocation

4. Have normal peristomal skin (as defined by a DET score = 0 or a DET score > 0 due to normal post-operative healing and/or scar tissue) at study enrollment  
Note: Subjects with suture granulomas or any other peristomal skin complication are not eligible for enrollment.
5. Able to provide an informed consent for study participation
6. Willing to follow protocol procedures, including attending in-person visits, as demonstrated by signing the informed consent

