#### 9.8 SUBJECT VISITS AND EVALUATION METHODS

The subject is enrolled into the eight (8) week [REDACTED] comprised of the Initial [REDACTED] Visit, the Mid-[REDACTED] Visit, and the Final [REDACTED] Visit. If during the [REDACTED] the subject experiences a PSC, they are immediately moved into the four (4) week [REDACTED] which is comprised of a Mid-[REDACTED] Visit, and a Final [REDACTED] Visit. An extra visit at any point during the study may also be necessary. Procedures for each visit are [REDACTED] listed in [REDACTED]

[REDACTED]

[REDACTED]

[REDACTED]

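### Does the PSC definition wrongly count DET increases that are due only to normal healing or scarring?

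*Combined protocol and SAP*

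**What the plan says.** Section 2.0 joins two limbs with an 'or'. The first is a DET score above 0 for any reason except ordinary post-surgical healing or scarring. The second is "or an increase in the subject's DET score as compared to the DET score at the prior visit as determined by a study investigator". Section 7.0 repeats both limbs and ends the second as "or an increase in the subject's DET score as compared to the DET score at the previous visit", without mentioning who decides.

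Inclusion criterion 4 in Section 8.1 accepts as normal skin at enrolment either DET 0 or "a DET score > 0 due to normal post-operative healing and/or scar tissue". Criterion 3 admits subjects up to 12 weeks after surgery.

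The definition has two uses. Section 5.2 makes it the secondary endpoint: "The secondary objective of the study is to compare incidence of PSCs in subjects using" the test barrier with those using control. Under Section 9.8, subjects who have a PSC in the eight-week phase are affected at once: "they are immediately moved into the four (4) week" phase that follows. Section 7.0 gives the overall limit: "the total possible time of participation in the study is up to 12 weeks and up to 5 scheduled study visits".

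For data capture, Section 7.0 lists "the Investigators evaluation of the subject's peristomal skin at all in-person visits" and adds: "Each clinical evaluation consists of a visual assessment of the stoma and peristomal skin, rating on the DET scale [1], and photographs". Section 9.6 blinds site personnel and subjects to the assigned barrier.

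**The concern.** The exclusion of healing and scarring is attached to the first limb only. For a subject at DET 0, any score above 0 is an increase, so a scar-only score left out by the first limb comes back through the second. On that reading the exclusion protects only subjects whose healing or scar score stays level or falls. That sits awkwardly with criterion 4, which treats such skin as normal at entry. In a recently operated population, these changes are plausible during follow-up.

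Two investigators could then classify the same skin differently, each within the protocol. Events unrelated to the barrier would be added to both arms, pulling the two incidences together and costing power. The secondary endpoint also set the initial sample size: 93 completed per arm, against 72 for the primary (Section 13.1). No visible analysis separates events by cause or by limb.

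**Working it through.** **1. The text side by side.**
- Criterion 4 describes skin at enrolment. It does not say that a later increase in DET is normal.
- The first limb stops a subject who enters with a healing or scar score from being an event on that score alone.
- The second limb asks whether the score has since risen.
- Together they form a workable rule: tolerate what was there at entry and count what gets worse. In Section 2.0 the closing phrase about the investigator can govern both limbs, which leaves room for judgement of cause.

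**2. The plan's own figure.** The PSC rates behind 93 per arm are blacked out, so the figure cannot be reproduced from the plan's inputs. Several pairs fit it. One is 50% versus 30% with the stated 2.5% read as one-sided (two-sided 5%) and 80% power:

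n = [1.960·√(2·0.40·0.60) + 0.842·√(0.50·0.50 + 0.30·0.70)]² / 0.20² ≈ 93.

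This pair is an assumption for illustration, not the sponsor's.

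**3. Dilution.** Let p be an arm's PSC rate without healing- or scar-only events, and f the share of the remaining subjects who have such an event, equal in both arms. The counted rate is q = p + (1 − p)f, so

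q₁ − q₂ = (1 − f)(p₁ − p₂).

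Power = Φ{[(q₁ − q₂)√n − z·√(2q̄(1 − q̄))] / √(q₁(1 − q₁) + q₂(1 − q₂))}, where q̄ is the mean of q₁ and q₂.

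Example, f = 5% and n = 105: q₁ = 0.525, q₂ = 0.335, difference 0.190, q̄ = 0.43. Power = Φ[(0.190·10.247 − 1.960·0.700)/0.687] = Φ(0.836) ≈ 79.9%.

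| f | Risk difference (points) | Power, 93/arm | Power, 105/arm | Healing-only events, 210 subjects |
|---|---|---|---|---|
| 0 | 20.0 | 80.0% | 84.6% | 0 |
| 1% | 19.8 | 79.0% | 83.7% | 1.3 |
| 2% | 19.6 | 78.0% | 82.7% | 2.5 |
| 5% | 19.0 | 74.8% | 79.9% | 6.3 |
| 10% | 18.0 | 69.5% | 74.8% | 12.6 |

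The last column is 105 × (0.5 + 0.7) × f.

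**4. Range of assumptions.** Control rates of 30, 40, 50 and 60% were taken, with test rates solved for 80% power at 93 per arm:
- 13.2, 21.2, 30.0 and 39.6% at two-sided 5%;
- 11.8, 19.5, 28.1 and 37.6% at two-sided 2.5%.

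Over these eight cases, the power ranges are:

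| f | 93/arm | 105/arm |
|---|---|---|
| 1% | 77.9–79.2% | 83–84% |
| 2% | 75.7–78.4% | 81–83% |
| 5% | 69.3–75.8% | 75–81% |
| 10% | 59.3–71.5% | 65–77% |

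**5. Direction.** With equal f and equal underlying PSC rates, q₁ = q₂, so the test keeps its size. The effect is dilution only.

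**6. The phase move.** A flagged subject is already an event, so the move does not alter the count as defined. A flag at week t gives DET ratings to about week t + 4 (8 + 4 = 12 weeks, the stated maximum). Follow-up falls short of week 8 only if t is below 4, and this matters only to an analysis that takes such events out again.

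**The case for a change.** The strongest case for acting is that the asymmetry is plain in both sections, that Section 7.0 lacks the phrase about the investigator, and that the phrase says who judges rather than which causes count. The first limb already needs a judgement of cause, so recording cause would be cheap. One added sensitivity analysis, with the main endpoint left alone, would show whether the result depends on these events.

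The textual point stands: the plan does not say whether the second limb is free of cause. The rest carries less weight.
- Keeping the definition for the main analysis leaves every power loss in the tables where it is, so the added analysis does not cure the harm.
- That analysis has problems of its own. It needs retrospective attribution for events already recorded. Letting a later increase of unclear cause count for most subjects, but not for those with an earlier healing-only flag, would be inconsistent. Flagged subjects also have two scheduled visits in four weeks against two in eight, so detection differs.
- The published text runs from 13.1 to 13.5, and the visit forms are blacked out. A rule on cause, or a field recording it, may already exist there, so its absence cannot be held against the plan.

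**Conclusion.** No change to the plan follows. The wording leaves a small gap that blinded investigators and analysts can fill sensibly, and it can equally be read as a deliberate rule that later worsening counts. A sentence on intent would be tidy, but no stated figure or analysis is shown to be wrong without it.

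Under the illustrative 50% versus 30%, the cost is 1 to 2 points of power at f of 1–2%. Across the eight cases at 93 per arm it is about 1 to 4 points, and at 105 per arm power stays above 80% at those values of f. A larger f would cost more: in the illustrative case the loss at 93 per arm reaches 5 points at f = 4.8%. Nothing in the documents points to a value that high or rules it out. The 105 per arm was set to hold conditional power (Section 13.5), so its margin over 93 is not guaranteed slack.

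This rests on equal frequency of such events in both arms, which randomisation and blinding make plausible, and on assumed PSC rates. If the planning rates used the definition as written, there is no loss against plan. No effect on the cost endpoint is claimed.

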### 3.0 ETHICS

- 3.1 The study and any amendments will be reviewed by an EC or IRB.
- 3.2 The study will be conducted in accordance with the ethical principles that have their origins in the Declaration of Helsinki.
- 3.3 This non-significant risk clinical study, including the Informed Consent, will be reviewed by an EC in the EU in accordance with MEDDEV, the IRB in Canada, and the IRB in the US in accordance with Title 21 of the Code of Federal Regulations, Parts 50 and 56. EC/IRB approval will be obtained prior to study initiation at the study site.

### 4.0 BACKGROUND/RATIONALE

PSCs are common and have been reported to be the reason for over 30% of the visits to an outpatient stoma clinic [2]. Peristomal skin problems can cause pain and reduce life satisfaction, and in addition, contribute to higher ostomy product usage, which may raise healthcare costs [3], [4]. It is evident, that maintaining and restoring the integrity of the peristomal skin has important implications.

Hollister Incorporated is marketing a new ostomy product [REDACTED] skin barrier is designed to maintain adhesive properties [REDACTED]

The purpose of this study is to demonstrate how the use of [REDACTED] impacts stoma related cost of care and peristomal skin condition. It is hypothesized that the [REDACTED] barrier improves peristomal skin condition by reducing the incidence [REDACTED] of PSCs which would manifest itself as an overall reduction in the stoma related cost of care.

## 5.0 STUDY OBJECTIVES

### 5.1 PRIMARY OBJECTIVE

The primary objective of the study is to compare stoma related cost of care for subjects using [REDACTED] to subjects using the control barriers [REDACTED].

### 5.2 SECONDARY OBJECTIVE

The secondary objective of the study is to compare incidence of PSCs in subjects using [REDACTED] to subjects using the control barriers [REDACTED].

## 6.0 STUDY PRODUCTS

### 6.1 STATUS OF STUDY PRODUCTS

The study barriers used in this protocol are Class I ostomy medical devices. Ostomy barriers are medical devices that: (1) are not intended as implants and do not present a potential for serious risk to the health, safety, or welfare of a subject; (2) are not purported or represented to be for use in supporting or sustaining human life; (3) are not for a use of substantial importance in diagnosing, curing, mitigating, or treating disease, or otherwise preventing impairment of human health; or (4) do not otherwise present a potential for serious risk to the health, safety or welfare of a subject. By this definition ostomy barriers are non-significant risk devices.

### 6.2 IDENTITY OF PRODUCT(S), PACKAGING AND STORAGE, TEST METHODS, PROCEDURES FOR RELEASE

Study barriers will be labeled with either of the following two labels, depending on if [REDACTED] is sold in that country and available in the

country's language, as necessary [REDACTED]

Hollister Incorporated  
[name] USA  
Protocol 5787-O

EC REP

Hollister ULC  
Ballina Ireland

LOT \_\_\_\_\_

*CAUTION: For study use only*

Hollister Incorporated  
[name] USA  
Protocol 5787-O

EC REP

Hollister ULC  
Ballina Ireland

LOT \_\_\_\_\_

*CAUTION: For study use only*

[REDACTED]

Study materials are supplied non-sterile. Subjects are provided up to a twelve (12) week supply of ostomy barriers in a flat or convex design [REDACTED]

[REDACTED] Subjects are also instructed to bring any unused study barriers and pouches with them to in-person study visits.

The control barrier material is [REDACTED], depending on the Investigator's standard of care and the subject's needs, and the test barrier

material is [REDACTED]. Subjects are instructed to wear the study barriers consecutively and according to their clinician recommended changing habit throughout the study period. The Investigators are to rely on clinical judgment to determine whether a subject requires a flat or convex barrier and [REDACTED] barrier material. If deemed necessary, Investigators may switch subjects between the flat and convex barriers of the same barrier material at any point during the study as well as adjust the stoma opening size or barrier flange size.

Currently marketed Hollister pouches are provided by the manufacturer. Accessories, [REDACTED], can be used as needed but are not provided as study products. If a site or subject does not have access to a barrier ring other than the [REDACTED], an alternative barrier ring can be provided by the Sponsor.

#### 6.3 RESPONSIBILITY FOR PRODUCT CONTROL, RETURN AND DISPOSAL

Used study barriers are discarded according to the subjects' normal practice. Any unused study barriers are returned to the Investigator at each visit. The Investigator is to maintain product accountability for dispensed and returned study barriers [REDACTED]. Unused study barriers are then either returned to the Sponsor or destroyed according to Sponsor's directions at the end of the study.

#### 6.4 INSTRUCTIONS FOR USE OF STUDY PRODUCT

The study barrier is self-applied by subjects and used according to the [REDACTED] provided in each box. It is the responsibility of the Investigator to make sure that the subject fully understands the Instructions for Use and the [REDACTED].

## 7.0 STUDY DESIGN

The study is multi-center, randomized, controlled, double-blinded, and utilizes an adaptive design.

Subjects who meet the Eligibility Criteria (listed in Sections 8.1 and 8.2) are enrolled and randomized to Arm 1 or Arm 2 during the Initial [REDACTED] Visit. The assigned Arm and the study barrier are double blinded. All subjects receive standard clinical management of stoma needs as per the Investigator's usual practices. Subjects are initially enrolled into the [REDACTED] which consists of two study visits after enrollment [REDACTED]. If the subject develops a PSC, as defined as a DET score greater than 0 due to anything other than normal post-operative healing and/or scar tissue, or an increase in the subject's DET score as compared to the DET score at the previous visit, prior to the end of the [REDACTED], the subject will be immediately moved to the four (4) week [REDACTED].

which consists of two study visits [REDACTED]. Thus, the total possible time of participation in the study is up to 12 weeks and up to 5 scheduled study visits.

Subjects in Arm 1 are assigned to the [REDACTED] barrier (Test) and subjects in Arm 2 are assigned to either the [REDACTED] barrier (Control).

Study visits consist of a physical evaluation and photography of the stoma area with the pouching system removed [REDACTED], a structured interview by the investigator or designee [REDACTED], and subject completion of a paper or online Quality of Life questionnaire [REDACTED] provided in the subject's local language. The duration of each study visit is approximately 30 minutes.

In support of the primary objective, the following utilization information is collected to support cost of care calculations: utilization of treatments related to stoma and/or PSCs (topical medications, clinic visits and accessory use), social impact of stoma and/or PSCs (missed work/appointments), stoma and/or PSC related hospitalizations, ER visits, physician/clinic visits, medication use and therapies, and barrier utilization (not including pouch utilization). This data is collected at each study visit through the use of [REDACTED] and may include documentation on [REDACTED].

In support of the secondary objective, the following clinical information is collected: the Investigators evaluation of the subject's peristomal skin at all in-person visits, including the [REDACTED] Visits, [REDACTED] Visits and any extra visits, if necessary. Each clinical evaluation consists of a visual assessment of the stoma and peristomal skin, rating on the DET scale [1], and photographs. This data is collected using [REDACTED].

[REDACTED]

## 8.0 STUDY SUBJECTS

### 8.1 INCLUSION CRITERIA

1. At least 18 years of age
2. Have a colostomy, ileostomy, or urostomy
3. Less than or equal to 12 weeks post-op from stoma creation or stoma relocation

4. Have normal peristomal skin (as defined by a DET score = 0 or a DET score > 0 due to normal post-operative healing and/or scar tissue) at study enrollment  
Note: Subjects with suture granulomas or any other peristomal skin complication are not eligible for enrollment.
5. Able to provide an informed consent for study participation
6. Willing to follow protocol procedures, including attending in-person visits, as demonstrated by signing the informed consent

## 8.2 EXCLUSION CRITERIA

1. Have a fistula, wound (e.g. mucocutaneous separation), lesion or suspected infection in the peristomal area
  2. Have known tape allergies
  3. Pregnant, planning to become pregnant, or lactating (as determined by interview only)
  4. Unwilling to discontinue use of [REDACTED] for the duration of the study.
  5. Uses topical steroids on peristomal skin at study enrollment
  6. Unable to wear a standard size 2-piece ostomy barrier
  7. Unable to read and understand local language
  8. Current living situation is long term care facility.
  9. Unable to discontinue use of [REDACTED] for the duration of the study.
- [REDACTED]

## 8.3 SUBJECT TREATMENT AND CARE

Subjects wear the study barrier and perform their peristomal skin care according to their normal daily routines and Investigator recommendations. All subject care is consistent with standard health care practices. No treatment is withheld during the course of the study (therapies, peristomal skin treatments, etc.).

## 8.4 DISCONTINUATION OF SUBJECTS FROM THE STUDY

[figure not shown]
Subjects must be informed of their right to discontinue from participation in the study at any time without prejudice. The Investigator may choose to discontinue a subject from the study. Reasons for a subject discontinuation may include the occurrence of an adverse event, significant protocol deviation, non-compliance, development of a concurrent illness or change of medication that would put the subject at increased risk or invalidate the results of the study. [REDACTED]

In addition Sponsor may end the study at any time.

Any new information gained during the study that might affect the subject's desire to continue participation will be conveyed to them in a timely manner.

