#### 9.11 PROCEDURES FOR SUBJECT DISCONTINUATION

Subjects electing to discontinue from the study for personal or other reasons are required to return all study materials and may be requested to schedule a final evaluation visit. The discontinuation of any subject following the Initial [REDACTED] Visit is documented using [REDACTED].

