## 10.0 ADVERSE EVENTS

### Anticipated Adverse Events

There is a small possibility that the subject may experience low level irritation of the peristomal skin. [REDACTED]

[REDACTED] Moderate or severe irritation is an anticipated Adverse Event.

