### Handling of Adverse Events

Upon study enrollment, all subjects are informed to notify the Investigator immediately if they experience any study-related problems. The Investigator will determine if an adverse event has occurred and if it was related to the study barrier and the stoma and/or skin around the stoma. Adverse events are documented on [REDACTED] within the EDC system. The Investigator indicates if the adverse event is related to the study barrier by marking "possibly", "probably", or "definitely" on the Adverse Event Form. The Investigator also indicates if the Adverse Event is related to the stoma and/or peristomal skin. Subjects who report health problems may be directed to seek care from their healthcare provider or emergency room as appropriate.

All Adverse Events are followed to determine resolution [REDACTED] by the Investigator and the Adverse Event form is updated to indicate date of resolution. If at any point, the Investigator determines the subject should no longer remain on the study barrier, the subject should be discontinued from the study.

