### 12.2 ANALYSIS POPULATIONS

#### Intent-to-treat (ITT)

The ITT population will consist of all enrolled subjects who have been randomized to a study arm. Subjects will be analyzed in the arm to which they were randomized regardless of whether they received the assigned treatment and irrespective of any protocol deviations or violations.

[REDACTED]

[REDACTED]

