### 12.3 INCOMPLETE FOLLOW-UP AND MISSING DATA

In the event that a subject does not complete the full eight weeks of the [REDACTED], or in the event of a PSC the full four weeks of the [REDACTED], the complete set of data available for that subject prior to loss-to-follow-up will be used for analysis. If there is missing data, there will be no imputation performed.

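### Stopping the barrier or deviating from protocol can end follow-up of subjects who stay in the ITT analysis, so later cost data are lost avoidably

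*Combined protocol and SAP*

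**What the plan says.** Section 8.4 gives the investigator discretion to discontinue a subject from the study. "Reasons for a subject discontinuation may include the occurrence of an adverse event, significant protocol deviation, non-compliance" is how the list of grounds opens. It ends with concurrent illness or a "change of medication that would put the subject at increased risk or invalidate the results of the study". The wording permits removal and does not require it. Text directly after the list is redacted.

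Section 10.0 (Handling of Adverse Events) is more directive. If the investigator "determines the subject should no longer remain on the study barrier, the subject should be discontinued from the study". This sentence is fully visible.

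On the analysis side, 12.2 keeps every randomized subject in the assigned arm, whether or not treatment was received and "irrespective of any protocol deviations or violations". For incomplete follow-up, 12.3 says "the complete set of data available for that subject prior to loss-to-follow-up will be used for analysis" and "If there is missing data, there will be no imputation performed". Section 9.11 provides that subjects who elect to leave "may be requested to schedule a final evaluation visit". No visible text separates stopping the barrier from stopping follow-up, or requires cost or DET data after discontinuation.

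**The concern.** The grounds in 8.4 are of two kinds. Some protect the subject. Others (deviation, non-compliance, invalidating the results) are meant to protect the data. Under an ITT analysis the second kind does not work: the subject is still analysed, with less information.

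The exits may also be related to outcome. The trial's hypothesis in 4.0 is that better skin lowers stoma-related cost. Section 10.0 states: "Moderate or severe irritation is an anticipated Adverse Event". If irritation leads the investigator to stop the barrier, the subject leaves the study just when extra visits, medication and product changes may add cost. Following adverse events to resolution, as 10.0 requires, is not stated to include resource use or DET.

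At stake is the completeness of the primary endpoint. The hypotheses in 13.1 concern total cost over 12 weeks and the ANCOVA uses mean daily cost. For an early leaver, both would rest on the days before exit.

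**Working it through.** **1. Removal against retention under the plan's own rules**

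- Deviating subject, removed: in the ITT population (12.2), data to exit only (12.3).
- Deviating subject, retained: in the ITT population, data to the planned end. The deviation is recorded under 9.10 and pertinent concomitant therapy under 9.7.
- Barrier stopped, subject removed (10.0): in the ITT population, data to exit only.
- Barrier stopped, subject retained: in the ITT population, data to the planned end. The safety purpose is already met by stopping the barrier.

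Membership of the ITT population is the same in each pair and only the amount of data differs. If a redacted second population excludes deviators, that can be done at analysis without ending follow-up.

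**2. Which data are lost**

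Section 2.0 defines a PSC as a DET score above 0 not due to normal healing or scar, or a rise in DET since the prior visit. Subjects are told to call if their skin changes (9.9), and DET is rated at extra visits too (7.0). Irritation bad enough to stop the barrier would therefore ordinarily be recorded as a PSC first. PSC incidence is then already captured, and what is lost is later cost. Later DET data matter for incidence only when a subject is removed before a PSC, for example for non-compliance.

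**3. Follow-up at stake (7.0, 9.8)**

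The plan's maxima reproduce: 8 + 4 = 12 weeks, and 1 + 2 + 2 = 5 scheduled visits. After a PSC at week s, planned follow-up ends at s + 4, so exit at the PSC loses 4/(s + 4) of it:

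- s = 4: 4/8 = 50%
- s = 8: 4/12 = 33%

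**4. Could this bias the comparison? (illustration, all inputs assumed)**

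Set daily cost before exit to 1 in both arms. Let a fraction q of an arm leave after a share t of follow-up, with daily cost r after the barrier is stopped. With full follow-up the arm mean is 1 + q(1 − t)(r − 1), so the arm difference is (q_test − q_control)(1 − t)(r − 1). Data truncated at exit show 0.

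- q = 15% vs 5%, t = 0.5, r = 1.5: 0.10 × 0.5 × 0.5 = 0.025, or 2.5% of baseline daily cost
- same, r = 3: 0.10 × 0.5 × 2 = 0.10, or 10%
- equal q and equal r in both arms: 0
- q reversed between arms: same size, opposite sign

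The documents give no exit rate, exit time or post-exit cost, so this shows only that a bias is possible.

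**5. Burden and reach of a change**

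Remaining visits after the initial one: 5 − 1 = 4 with a PSC, 3 − 1 = 2 without. At about 30 minutes each (7.0) that is at most 4 × 0.5 = 2 h, or 2 × 0.5 = 1 h.

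The revised size is 2 × 105 = 210. The first interim is already done. Section 13.1 mentions 92 subjects without saying whether per arm, and 13.5 reads as 92 in each arm, with a redaction after the number.

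- 92 in total: 210 − 92 = 118 not yet finished
- 92 per arm: 210 − 184 = 26 not yet finished

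The further look planned at 76 (±5) per arm fits the first reading better, since 92/2 = 46 is below 76 and 92 is above it. If 2%, 5% or 10% (assumed) of these would otherwise be removed, the change retains about 2.4, 5.9 or 11.8 of 118, or 0.5, 1.3 or 2.6 of 26. At the 2 h maximum that is up to 23.6 or 5.2 visit-hours in all.

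**The case against.** The strongest reply is that this is common, permissive discontinuation language and no harm is shown. Much of that stands.

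- **No contradiction.** A reader might infer that 8.4 conflicts with 12.2. It does not: one governs participation and the other governs analysis.
- **Removal is not pure loss.** A reader might infer that discontinuation protects nothing and only loses data. That is too strong. The safety grounds protect subjects, data before exit count towards mean daily cost, and 9.11 allows a final visit. That visit is optional, however, and is written for subjects who choose to leave.
- **The route is narrow.** Ordinary skin treatment (8.3), as-needed accessories and flat/convex switches (6.2) are permitted, so routine PSC care is not a deviation.
- **Redaction.** Text after the 8.4 list, around the population definitions in 12.1 and 12.2, and in the visit procedures is blacked out and could qualify 8.4. The sentence in 10.0 carries no visible qualification.
- **Blinding.** It makes arm-aware removal less likely. It cannot rule out unequal exits caused by how the barriers perform.
- **Limited yield.** The trial is well under way, and no wording recovers data from subjects who stop attending.

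None of this supplies a reason to stop following a consenting subject who remains in the ITT analysis.

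**Conclusion.** The point holds as a low-priority, avoidable loss of data. Ending follow-up for deviation, non-compliance or supposed invalidation of results, or because the barrier was stopped, brings no benefit to the ITT analysis and discards later data, chiefly stoma-related cost.

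A reader might go further and infer that the primary result is biased, perhaps towards the test barrier, or that PSC incidence is materially understated. The documents support neither. Size and direction cannot be derived without exit rates and timing by arm, and skin-related barrier stops would ordinarily follow a recorded PSC. The plan's sample sizes are not in question here.

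The conclusion assumes that no redacted text already requires follow-up after discontinuation.

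**What to change.** Three wording changes, with EC/IRB approval:

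- **10.0:** a subject for whom the barrier is no longer suitable is discontinued from the study barrier, not from the study.
- **8.4:** remove significant deviation, non-compliance and invalidation of results as grounds for ending follow-up. Keep subject safety and the subject's own withdrawal.
- **8.4 and 9.11:** add, for example, *Subjects who stop the study barrier or deviate, and who still consent, attend all remaining scheduled visits, with resource use and DET collected to the planned end. Non-study barriers used are recorded. Deviations are documented and do not by themselves end follow-up.*

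The cost is amendment work, at most about 2 h of visit time per retained subject, and the capture and costing of non-study barriers. The last item needs explicit provision because visible product accountability (6.3) covers only study barriers, while barrier use is part of the primary cost. The change helps only subjects not yet finished and recovers nothing from those who stop attending or withdraw consent.
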